6. CCI [REDACTED]
[REDACTED]
[REDACTED]
8. When a respiratory flare is suspected during the study period based on investigator's judgement.
9. CCI [REDACTED]
[REDACTED]
10. When a CV flare is suspected during the study period based on investigator's judgement.
11. Only SAEs that are considered related to study procedures are to be collected from the time of signing informed consent.
12. Vital sign measurements will include temperature, systolic and diastolic blood pressure, and heart rate.
13. During the treatment period, all laboratory samples should be obtained pre-dose.
14. Eosinophil count samples for the screening visit only may be analysed by local labs if required. If a local sample is required, it is important that a sample for central analysis is obtained at the same time. Local lab eosinophil count results performed at the screening visit will be entered to the eCRF. If local lab samples are taken, a second sample will also be sent for central testing. The higher of the eosinophil cell count values is to be used to fulfil the entry criteria for enrolment.
15. Do not perform for each discontinuation visit, follow test frequency of Treatment Period schedule visit 2-15.
16. Negative urine pregnancy test result must be confirmed prior to dosing in female participants of reproductive potential. If a urine test cannot be confirmed as negative (e.g., an ambiguous result), a serum pregnancy test is required. In such cases, the participant must be excluded from participation if the serum pregnancy result is positive.
17. Pregnancy testing is only required until the end of systemic exposure, 12 weeks after the last dose.
18. Urine tests are done locally using dipstick. If found abnormal, the urine sample will be sent to the central laboratory for further testing.
19. If test was performed within 3 months prior to Visit 2, testing at Screening is not required. Test required are hepatitis B surface antigen and hepatitis C antibody. Participants with positive hepatitis C antibody due to prior resolved disease can be enrolled only if a confirmatory negative hepatitis C RNA test is obtained.
20. If no documented results are available.
21. For participants who discontinue treatment immunogenicity is to be performed 4 and 12 weeks after the last dose only.
22. For participants who discontinue treatment PK is to be performed 4 weeks after last dose only.
23. The date and time of the administration of study treatment will be recorded in the eCRF.

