1.3. Schedule of Activities (SoA)

The Schedule of Activities (SoA) is presented in [Table 1](#).

CONFIDENTIAL

215360
Protocol Amendment 4 Final

Table 1 Schedule of Activities

Procedures	Screen	Treatment Period and Exit Visit ¹															Early discontinuation /Withdrawal Visit		Follow-up
Study visit	1	2	3	4	5	6	7	8	9	10	11	12	13	14	15 Exit visit	Flare ²	Discontinue from study treatment Visit (replacing visits 2-15) ³	Withdrawal Visit	16
Study week	-2 to -4	0	4 (±7 days)	8 (±7 days)	12 (±7 days)	16 (±7 days)	20 (±7 days)	24 (±7 days)	28 (±7 days)	32 (±7 days)	36 (±7 days)	40 (±7 days)	44 (±7 days)	48 (±7 days)	52 (±7 days)				~12 wks After last dose (±7 days)
Informed consent ⁴	X																		
Eligibility assessments																			
Inclusion/Exclusion criteria	X	X																	
Demography/childbearing status assessment	X																		
Medical and treatment history	X																		
Parasite screening ⁵	X																		
Physical examination including height and weight	X							X							X				
Efficacy assessments																			
CCI																			
Concomitant medications including OCS		X	X	X	X	X	X	X	X	X	X	X	X	X	X	X	X	X	X
CCI																			
BFI item 3 ⁶																			
CCI																			

CONFIDENTIAL

215360
Protocol Amendment 4 Final

Procedures	Screen	Treatment Period and Exit Visit ¹															Early discontinuation /Withdrawal Visit		Follow-up
Study visit	1	2	3	4	5	6	7	8	9	10	11	12	13	14	15 Exit visit	Flare ²	Discontinue from study treatment Visit (replacing visits 2-15) ³	Withdrawal Visit	16
Study week	-2 to -4	0	4 (±7 days)	8 (±7 days)	12 (±7 days)	16 (±7 days)	20 (±7 days)	24 (±7 days)	28 (±7 days)	32 (±7 days)	36 (±7 days)	40 (±7 days)	44 (±7 days)	48 (±7 days)	52 (±7 days)				~12 wks After last dose (±7 days)

CCI

Safety assessments

AE/SAE assessment	X ¹¹	X	X	X	X	X	X	X	X	X	X	X	X	X	X	X	X	X	X
Vital signs ¹²	X	X						X							X	X		X	
ECG	X														X	X			

Laboratory assessments¹³

Haematology with differential	X ¹⁴	X	X	X	X	X	X	X	X	X	X	X	X	X	X	X	X	X	
Clinical and liver chemistry	X	X			X			X			X			X		X	X ¹⁵	X	
Pregnancy test ¹⁶	X	X	X	X	X	X	X	X	X	X	X	X	X	X	X		X ¹⁷	X	X
Urinalysis ¹⁸	X														X		X ¹⁵	X	
Hepatitis serology ¹⁹	X																		
Total IgE		X																	
F/P status ²⁰	X																		
T-cell profile	X																		
Immunogenicity		X						X							X		X ²¹	X	X
PK sample			X					X							X		X ²²	X	
IL-5		X																	

Investigational product

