Study treatment administration ²³		X	X	X	X	X	X	X	X	X	X	X	X	X					
--	--	---	---	---	---	---	---	---	---	---	---	---	---	---	--	--	--	--	--

CONFIDENTIAL

215360
Protocol Amendment 4 Final

Procedures	Screen	Treatment Period and Exit Visit ¹															Early discontinuation /Withdrawal Visit		Follow-up
Study visit	1	2	3	4	5	6	7	8	9	10	11	12	13	14	15 Exit visit	Flare ²	Discontinue from study treatment Visit (replacing visits 2-15) ³	Withdrawal Visit	16
Study week	-2 to -4	0	4 (±7 days)	8 (±7 days)	12 (±7 days)	16 (±7 days)	20 (±7 days)	24 (±7 days)	28 (±7 days)	32 (±7 days)	36 (±7 days)	40 (±7 days)	44 (±7 days)	48 (±7 days)	52 (±7 days)				~12 wks After last dose (±7 days)
eCRF and eDiary																			
Register visit in IVRS	X	X	X	X	X	X	X	X	X	X	X	X	X	X	X		X	X	
Complete eCRF	X	X	X	X	X	X	X	X	X	X	X	X	X	X	X		X	X	X
eDiary registration and training	X																		
Dispense (D)/collect (C) eDiary	D ²⁴														C			C	
Review of eDiary ²⁵		X	X	X	X	X	X	X	X	X	X	X	X	X	X		X	X	

Abbreviations: AE, adverse event; BFI, Brief Fatigue Inventory; ECG, electrocardiogram; eCRF, electronic case report form; F/P, FIP1L1-PDGFRα fusion tyrosine kinase gene translocation; HCRU, healthcare resource utilisation; HES, hypereosinophilic syndrome; IgE, Immunoglobulin E; IL-5, Interleukin-5; IVRS Interactive Voice Response Systems; OCS, oral corticosteroid(s); **CCI**; RNA, ribonucleic acid; SAE, serious adverse event; **CCI**.

- Activities that will be performed only in clinic are greyed out. All participants will need to attend a clinic visit at Screening (Visit 1), Baseline (Visit 2), Week 4 (Visit 3), Week 8 (Visit 4), Week 24 (Visit 8), and the Week 52 exit visit (Visit 15). A Flare Visit follows routine medical practice. The other visits may be performed remotely where applicable country and local regulations and infrastructure allow. Eligibility criteria assessment data will all be captured on site. Data from efficacy assessments other than echocardiogram, ECG, and spirometry will be captured digitally via electronic devices and teleconferences or on site. Echocardiogram, ECG, and spirometry data will only be captured at site visits. Laboratory assessments other than haematology with differential, clinical and liver chemistry, pregnancy test, and PK samples are captured on site.

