4. STUDY DESIGN

4.1. Overall Design

This is a 52-week, open-label, single arm, multicentre study of mepolizumab SC in children and adolescent participants with HES receiving SoC therapy.

Participants will be aged 6 to 17 years at Screening (Visit 1) and are expected to remain in the study for 52 weeks. Approximately 15 participants who are on a stable dose of HES therapy for at least 4 weeks prior to Visit 2 will be enrolled. Participants will have a 2- to 4-week run-in period for training and compliance on the use of their eDiary to record daily assessments. Eligible participants will receive the first dose of mepolizumab at Visit 2.

All participants will need to attend a study-site visit at Screening (Visit 1), Baseline (Visit 2), Week 4 (Visit 3), Week 8 (Visit 4), Week 24 (Visit 8), and the Week 52 exit visit (Visit 15). The other visits may be performed remotely where applicable country and local regulations allow. Home healthcare services may also be utilised to support these activities where local regulations and infrastructure allow. The last dose of mepolizumab will be given at Week 48 and the final visit of the treatment period will be at Week 52. There is a follow-up visit 8 weeks after the Week 52 visit (12 weeks after the last dose of mepolizumab). Protocol-defined eligible participants may enter an EAP, where available, immediately after completion of the 52-week study period (Section 6.6). Participants who enter the EAP will not need a study follow-up visit.

All participants will be on active treatment with mepolizumab. Investigators may adjust HES therapy (SoC) as needed from Visit 3 (4 weeks after the first dose of mepolizumab). All participants will be managed during the study according to routine medical care (i.e., participants and/or caregiver will be instructed to contact their investigator for evaluation or seek emergency care as necessary if they or their child experience worsening of symptoms as per their usual practice).

The investigators will use the CCI [REDACTED] to assess for the presence of a HES flare.

An Independent Data Monitoring Committee (IDMC) will be utilised during the study.

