4.4. End of Study Definition

The total study treatment duration is 52 weeks.

The end of the study is defined as the date of the last visit of the last participant in the study. A participant is considered to have completed the study if he/she has completed the last visit at Week 52, regardless of whether mepolizumab treatment was received during the entire study period. For participants who do not enter the expanded access program (EAP), the end of the study (EOS) will be considered the follow-up visit (visit 16). For participants who enter the EAP before the follow-up visit has occurred, the end of study (EOS) will be considered Week 52 (visit 15).

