6.8. Concomitant Therapy

Participants will be permitted to continue their SoC HES therapy (concomitant therapy) throughout the study period. Starting at 4 weeks after the first dose of mepolizumab (Visit 3), investigators may adjust SoC doses as medically appropriate based on clinical symptoms and blood eosinophil counts.

Any medication or vaccine (including over-the-counter or prescription medicines, vitamins, and/or herbal supplements) that the participant is receiving at the time of enrolment or receives during the study must be recorded, along with:

- reason for use
- dates of administration including start and end dates
- dosage information including dose and frequency

Any investigational agents (biologic or non-biologic) are not allowed within the 30 days or 5 drug half-lives, whichever is longer, prior to Screening (Visit 1), and until Visit 15. The term “investigational” applies to any drug not approved for sale in the country in which it is being used or investigational formulations of marketed products. Anti-IL-5 and anti-IL-5-receptor therapies are not permitted to be used during the study (from Visit 1 until the end of study visit, See Section 4.4), whether investigational or non-investigational.

For participants who are required to complete the follow-up visit, prohibited medications, such as anti-IL-5 / IL-5 receptor therapy, must not be started until the follow-up visit is complete. The follow-up period is required to reflect the safety information after 12 weeks from the last IP dose.

In general, GSK study participants can be vaccinated against COVID-19 using vaccines authorised via limited regulatory mechanisms (e.g., Emergency Use Authorisation [EUA]) or approved via accelerated or full approval mechanisms.

Use of other candidate COVID-19 vaccines that have not received limited, accelerated, or full authorisation/approval, and are only in use as part of a clinical trial, are not allowed.

The study Medical Monitor should be contacted if there are any questions regarding concomitant or prior therapy.

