8.2.4. Clinical Laboratory Assessments

See [Appendix 2](#) for the list of clinical laboratory tests to be performed and to the SoA for the timing and frequency.

The investigator must review the laboratory report, document this review, and record any clinically significant changes occurring during the study in the AE section of the eCRF. The laboratory reports must be filed with the source documents.

Abnormal laboratory findings associated with the underlying disease are not considered clinically significant, unless judged by the investigator to be more severe than expected for the participant's condition.

All laboratory tests with values considered clinically significantly abnormal during participation in the study or within 4 weeks after the last dose of study intervention should be repeated until the values return to normal or baseline or are no longer considered significantly abnormal by the investigator or study Medical Monitor. If such values do not return to normal/baseline within a period of time judged reasonable by the investigator, the aetiology should be identified and the sponsor notified.

All protocol-required laboratory tests, as defined in Section 10.2, must be conducted in accordance with the laboratory manual and the SoA (Section 1.3).

If laboratory values from non-protocol-specified laboratory tests performed at the institution's local laboratory require a change in participant management or are considered clinically significant by the investigator (e.g., SAE or AE or dose modification), then the results must be recorded in the eCRF.

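### Participants who receive the Week 48 dose have no routine liver chemistry scheduled after it

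*Protocol*

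**What the plan says.** **Chemistry schedule.** In Protocol Section 1.3, Table 1, the row "Clinical and liver chemistry" is marked at Visits 1, 2, 5, 8, 11 and 14 and in the Flare, Discontinuation and Withdrawal columns. Visits 15 and 16 are blank.

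**Dosing.** The row "Study treatment administration" is marked from Visit 2 to Visit 14. Section 4.1 agrees: "The last dose of mepolizumab will be given at Week 48 and the final visit of the treatment period will be at Week 52".

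**Order of sample and dose.** Footnote 13 to Table 1: "During the treatment period, all laboratory samples should be obtained pre-dose".

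**Other tests at Visit 15.** Haematology, urinalysis, PK and immunogenicity are all marked there, and Section 4.1 makes it an on-site visit for everyone.

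**After the last dose.** Section 8.2.4 requires clinically significant abnormal laboratory values found "during participation in the study or within 4 weeks after the last dose of study intervention should be repeated until" they resolve or stop being a concern. Section 6.8 adds: "The follow-up period is required to reflect the safety information after 12 weeks from the last IP dose". SAP 6.2.2.3 counts adverse events as on-treatment up to 28 days after the last dose.

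**Use of the data.** SAP 4.7.3.1 plans laboratory summaries and plots of maximum ALT against baseline ALT and against total bilirubin.

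**The concern.** A participant who takes every dose and follows the schedule exactly contributes no liver result after the final dose. AEs are still collected at Visits 15 and 16, but a transaminase or bilirubin rise without symptoms needs a blood test to be seen. That includes a possible Hy's Law case, which Section 10.3.2 makes reportable as an SAE.

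Two features make this more than a matter of taste. First, the SAP treats the 28 days after the last dose as on-treatment for AEs, yet no routine chemistry covers those days in full-course participants. Second, the Withdrawal Visit takes chemistry and Visit 15 does not, so the closing liver measurement depends on how a participant leaves the study. With about 15 participants, the liver displays rest on few values per person.

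Symptoms are also an uncertain guide in this population. Section 8.3.2 warns that in children aged 6 to 11 non-specific symptoms may be all that shows of some adverse reactions. The Amendment 4 summary plans at least 11 of the 15 participants in that age group.

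**Working it through.** The plan gives no figure to reproduce. The check is one of visit timing.

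**Step 1: alignment of the table.** Table 1 has 19 visit columns. The rows for AEs, haematology, chemistry, urinalysis, immunogenicity, PK and dosing each have 19 cells, so nothing suggests that the chemistry marks have shifted. They follow a regular 12-week pattern.

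**Step 2: next routine chemistry after each dose.** Doses fall at Weeks 0, 4, ..., 48, which is 48/4 + 1 = 13 doses. Because sampling is pre-dose, a chemistry sample counts for a dose only if it comes at a later visit.

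| Doses at weeks | Next routine chemistry | Interval |
|---|---|---|
| 0, 4, 8 | Week 12 | 12, 8, 4 weeks |
| 12, 16, 20 | Week 24 | 12, 8, 4 weeks |
| 24, 28, 32 | Week 36 | 12, 8, 4 weeks |
| 36, 40, 44 | Week 48 | 12, 8, 4 weeks |
| 48 | none | - |

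Twelve of 13 doses are followed by routine chemistry within 4 to 12 weeks. The thirteenth is not.

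**Step 3: length of the gap (nominal visit dates).**
- To Visit 15: 52 − 48 = 4 weeks = 28 days. This is 28/364 = 7.7% of the treatment period, and the whole of the SAP's last dose + 28 days window.
- To Visit 16: 60 − 48 = 12 weeks = 84 days.
- A participant who enters the EAP before follow-up ends the study at Visit 15 (Sections 4.4 and 6.6), so the in-study gap is 4 weeks. For one who attends Visit 16 it is 12 weeks.

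**Step 4: data behind the maximum-ALT plots.** Without a Flare visit or unscheduled test, a full-course participant has four routine post-baseline results (Weeks 12, 24, 36 and 48), all drawn before the last dose.

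**Step 5: who still gets chemistry after a last dose.**
- Participants who stop treatment early but stay in the study: footnote 15 keeps them on the regular chemistry frequency. One whose last dose was at Week 44, for example, has the Week 48 sample 4 weeks later.
- Participants who withdraw: the Withdrawal Visit includes chemistry. SAP 6.2.4 moves withdrawal data to the next scheduled visit. For a withdrawal after Visit 14 that visit is Visit 15, where no completer has routine chemistry to set beside it.
- Participants with a Flare visit after Week 48: chemistry is marked there.
- Anyone with an abnormality at Week 48 that is being followed, or for whom the investigator orders a test.

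The group left without coverage is participants who receive the Week 48 dose, do not withdraw afterwards, and have none of these triggers.

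**The case against.** The case for leaving the schedule alone is reasonable in several respects.

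**Completers are a wider group.** A reader might infer that liver injury after the last dose is looked for in no completer at all. Section 4.4 does not support that: a completer is anyone who reaches Week 52, "regardless of whether mepolizumab treatment was received during the entire study period", and footnote 15 keeps early treatment discontinuers on chemistry. The point applies only to those who receive the Week 48 dose.

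**Detection does not depend on symptoms alone.** A reader might also infer that a rise would be found only if symptomatic. Flare visits include chemistry, Section 10.2 allows extra tests at any time, Section 8.2 allows added safety time points, and Section 10.5 requires weekly liver tests after a monitoring event. What stops is routine testing of participants without such a trigger.

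**There is no literal contradiction.** Section 8.2.4 says what to do with abnormal values that arise and does not promise a test. It covers all laboratory tests, and haematology and urinalysis fall at Week 52. The Section 6.8 sentence explains why prohibited medication must wait until follow-up, and Visit 16 does collect AEs, immunogenicity and pregnancy results. Neither section commits the plan to a liver test.

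**Size and rationale.** Twelve weeks is the protocol's own routine chemistry interval, and a Week 52 sample closes only 4 of the 12 weeks for those with follow-up. A withdrawal may come up to about 12 weeks after the last chemistry, whereas a completer was tested 4 weeks before exit, which could explain the different columns. Table 2 names no hepatic risk, and 12 doses have been followed by chemistry by Week 48.

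All of this limits the point without removing it. The safeguards need a trigger, and the schedule followed as written yields no liver result after the final dose in full-course participants.

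**Conclusion.** The point holds as a gap in coverage. For participants who receive the Week 48 dose, routine clinical and liver chemistry ends just before that dose: 1 of 13 doses has none after it, for 28 days in EAP entrants and 84 days in those attending follow-up. The documents do not allow a count of affected participants. It depends on how many of about 15 receive dose 13 and have no later trigger for a test.

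A reader might go further and say that the laboratory safety record as a whole stops at Week 48. It does not: haematology and urinalysis run to Week 52, and SAP 4.7.3.1 does not promise an end-of-treatment chemistry value. The statement is limited to routine chemistry.

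This is an inexpensive improvement that should be made. It is not a defect that undermines the trial, since the documents show no liver signal. The conclusion assumes nominal visit dates (visits carry ±7 days) and that the blank Visit 15 and 16 cells, read here from text extracted from the PDF, are blank in the original table.

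**What to change.** The sponsor should reconcile the Table 1 chemistry row with the Withdrawal Visit column, Section 8.2.4 and the SAP on-treatment window, either by justifying the blank cells or by aligning the schedule.

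The low-burden way to align it is to mark the existing chemistry panel at Visit 15, using the blood draw already scheduled at that mandatory site visit, and to include the result in the SAP 4.7.3.1 displays. This would cover the full 28-day window, but only the first 4 of the 12 weeks for participants with a follow-up visit. The sponsor should say whether the remaining 8 weeks are left without routine chemistry on purpose.

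For participants already past Week 52, the SAP and the clinical study report should state that routine chemistry ends at Week 48 pre-dose, so that the maximum-ALT plots are read accordingly.

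The cost is one mark in Table 1, a line in the SAP and a few mL of blood per participant. The added volume must first be checked against the 97 mL ceiling in Section 8. No dose, stopping limit or management rule changes.

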24. CCI [REDACTED]
[REDACTED]
[REDACTED]
25. Review AEs and participant questionnaires, identify HES flares and check questionnaire compliance.

2. INTRODUCTION

2.1. Study Rationale

Hypereosinophilic syndrome (HES) is a group of rare haematological disorders without a known cause in which eosinophils are overproduced in the bone marrow for prolonged periods of time. The sustained overproduction of eosinophils in the bone marrow results in high blood eosinophil counts (eosinophilia). When activated eosinophils from the bloodstream infiltrate various tissues, they cause inflammatory tissue damage and dysfunction. HES is only diagnosed when organ damage and/or dysfunction are present. The current definition and diagnosis of HES in patients uses the following criteria: (1) blood eosinophilia of >1500 eosinophils/ μL on 2 examinations (at an interval ≥ 1 month, except in case of life-threatening organ damage when diagnosis can be made immediately) and/or tissue eosinophilia; (2) organ damage and/or dysfunction attributable to tissue eosinophilia; and (3) exclusion of other disorders or conditions as the major reason for organ damage [Valent, 2012].

Mepolizumab

Eosinophilia is central to the pathophysiology of HES and interleukin-5 (IL-5) is a key cytokine regulating the lifecycle of the eosinophil. Neutralisation of IL-5 with an anti-IL5 monoclonal antibody, therefore, offers a potential therapeutic option for HES.

Mepolizumab is a humanised monoclonal antibody (immunoglobulin G1 [IgG1], kappa) that is specific for human IL-5. Mepolizumab blocks binding of human IL-5 to the alpha chain of the IL-5 receptor complex expressed on the eosinophil cell surface. In conditions where eosinophilia is considered to play an important part in the pathology, such as eosinophilic asthma, HES, eosinophilic granulomatosis with polyangiitis (EGPA), and chronic rhinosinusitis with nasal polyps (CRSwNP), a consistent reduction in blood eosinophil counts is observed in association with mepolizumab administration, with concomitant clinical improvement [Ortega, 2014; Pavord, 2012; Roufosse, 2020; Han, 2020; Wechsler, 2017]. Mepolizumab 300 mg SC administered every 4 weeks was recently approved in the United States, the European Union, and other countries for the treatment of HES.

Phase 3 Study 200622

In the pivotal Phase 3 study, 108 participants aged ≥ 12 years were treated for 32 weeks with either mepolizumab 300 mg SC or placebo SC every 4 weeks in addition to their stable HES standard of care (SoC) therapy. In this trial, mepolizumab 300 mg administered SC every 4 weeks was significantly effective in reducing HES flares, fatigue severity, and blood eosinophil counts compared with placebo when added to SoC therapy. CCI

[REDACTED]

[REDACTED]

[REDACTED]

[REDACTED]

[REDACTED]

CCI
[REDACTED]
[REDACTED]
[REDACTED]Open-label Extension Study 205203

During the open-label extension (OLE) study, CCI [REDACTED] were treated with mepolizumab 300 mg SC every 4 weeks for 20 weeks. CCI [REDACTED]
[REDACTED]
[REDACTED]
[REDACTED]
[REDACTED]
[REDACTED]
[REDACTED]
[REDACTED]

The purpose of this study is to investigate the efficacy and safety of mepolizumab SC in children (aged 6 to 11 years) and adolescents (aged 12 to 17 years) with HES who are receiving SoC therapy.

